4.1.1 Screening

During the initial contact, potential participants will be informed about the study and will be asked whether they would like to be screened for the study (see telephone/in-person recruitment script and telephone script for potential participants who self-refer). Parents/caregivers who are eligible will then be provided further information about the study as detailed in the recruitment procedures.

4.1.2 Enrollment/Baseline

Eligible caregivers who provide consent via REDCap will be presented with the baseline survey queue on REDCap. The baseline forms are expected to take about

45 minutes to complete. Once study staff receive complete baseline forms, participants will be randomly assigned to either IRC or R2R-TBI and will be sent a link, password, and instructions on how to access the R2R-TBI application or IRC website.

4.1.2.1 Obtaining Consent

Study staff will review the consent form with prospective participants (via phone or in-person; see phone/in-person recruitment script) and parents will have the opportunity to ask questions. Study staff will document this consent process on a form that will be included in the study binder. A waiver of documentation of consent will be requested for this study and study staff will accept participant acknowledgement on REDCap as consent for the study. (i.e., participants clicking “YES, I acknowledge that I have viewed the information sheet and am voluntarily choosing to participate in this study”). The consent form/information sheet will be viewable on REDCap prior to beginning baseline measures. All pertinent aspects of the study will be included in the information sheet, including, contact information of the researcher, study purpose, risks/benefits, confidentiality, and right to withdraw.

4.1.3 Study Groups

4.1.3.1 R2R-TBI Intervention

Caregivers assigned to the R2R-TBI intervention will receive a link to the web-based intervention as well as a username and password. Caregivers will receive weekly text, email, or phone reminders (participants will choose their preferred method of contact) to engage with the website. Time caregivers spend on the intervention as well as details on how often they log-on and devices used when accessing the intervention will be recorded.

The R2R-TBI intervention was developed to be interactive and encourage active participation. Caregivers choose their own navigation paths through the web platform, allowing them to tailor the program to their specific needs. To encourage active engagement, caregivers have opportunities to practice skills taught in the intervention (e.g., questions with multiple responses and immediate feedback) and the format of these activities is varied. Each of these different components were tested in the usability testing sessions, and caregivers reported ease of use.

Figure 1 provides a brief overview of the R2R-TBI modules. Each module is designed to take less than 20 minutes to complete and parents have access to all modules when they access the site. While we will encourage caregivers to move sequentially through the first four modules before selecting supplemental modules, feedback from the pilot trial suggests that caregivers benefit from flexibility to navigate to content that is most relevant for them. For example, parents with immediate school concerns or greater relationship concerns may want to access that content earlier. Note that participants in both conditions will continue to receive usual care.

Figure 1. Summary of R2R-TBI modules

MODULE 1: WHAT TO EXPECT?

Parents often desire information about potential outcomes and benefit from ongoing information which may help reduce parental distress (Savage et al., 2005, Prigatano & Gray, 2007). In this module, caregivers are provided information about TBI and common sequelae of injury. Caregivers may select and learn more about symptoms that their child is experiencing.

MODULE 2. PROBLEM SOLVING YOUR CHILD'S RECOVERY

Problem-solving therapy approaches show promise in improving outcomes among children and families impacted by chronic health conditions (Law et al., 2014). As parent/guardians adjust to their *new normal*, this module teaches skills and a problem-solving framework that has been successfully used by caregivers of children with TBI (e.g., Wade et al., 2014; 2018).

MODULE 3. POSITIVE PARENTING

Parents learn positive parenting skills such as how to set their child up for success, and strategies to strengthen the parent-child relationship, set boundaries, and manage externalizing behaviors. Parents are able to select information that is specific to their child's age and developmental level.

MODULE 4. TAKING CARE OF YOURSELF

Caregivers experience a lot of stress in the acute phase post injury, which can persist for many years. In this module, parents are taught stress management strategies such as progressive muscle relaxation, relaxed breathing, and guided imagery.

MODULE 5. WORKING WITH YOUR CHILD'S SCHOOL

Parent perspectives of quality of communication with their child's school during re-entry and affects child outcomes (Andersson et al., 2016). In this module, parents learn how to work collaboratively with the school to support their child's re-entry and needs. Information about services/supports (e.g., IEP, 504-Plan) is provided.

MODULE 6. GUILT, GRIEF, AND CAREGIVING

Parents of children with TBI often experience feelings of guilt and grief (Aitken et al., 2009; Kirk et al., 2015). This module works to normalize feelings of guilt and grief and shares experiences of other caregivers. Parents are provided strategies to manage difficult emotions and information on respite care and other services/support.

MODULE 7. PARENTAL COMMUNICATION

Parents learn about common relationship stressors following pediatric TBI (e.g., differing parental expectations, poor communication, financial concerns, etc.; Kirk et al., 2015). Parents also learn tips for improving communication with their spouse/partner and practice effective talking/listening skills.

MODULE 8. SLEEP ISSUES

Many children with TBI experience sleep difficulties (Sumpter et al., 2013). This module covers possible reasons for their child's sleep issues, and strategies for supporting healthy sleep for both child and parent.

MODULE 9. PARENTS AND SIBLINGS

Siblings of children with TBI are at risk of poorer psychological functioning and reduced quality of life (Sambuco et al., 2008). In this module, parents learn about typical sibling reactions and strategies they can use to support all their children. Parents are also taught to differentiate between normal sibling reactions and warning signs of more serious problems, as well as resources on services/supports for siblings.

MODULE 10. AFTER HIGH SCHOOL

This module is for parents of children with post-TBI challenges transitioning out of high school. It contains information on their child's legal rights around education and job training and links to organizations that

support transition, such as the State Vocational Rehabilitation Agency.

4.1.3.2 Internet Resources Condition (IRC)

Caregivers in the web-based resources condition will be provided with a link and password to a website that provides links to a range of resources on pediatric TBI including local, state, and national brain-injury associations. These resources will also be provided to families in the R2R-TBI intervention. Essentially, families in the IRC condition will have access to the same links to resources without the specific intervention content/modules. This will enable us to equate the groups with regard to access to information and resources available on the internet. Parents in this group will also have access to technical support as well as the opportunity to contact the researchers with any questions/concerns.

Participants in both conditions will continue to receive usual care.

4.1.4 Check-ins

Study staff will check-in with study participants at regular intervals during their participation in the study via phone calls, texts and/or emails. These check-ins will allow study staff to keep participants engaged and to provide reminders to use the website.

4.1.5 Follow-ups

Follow-up 1 (30 – 45 days after receiving study login)

Approximately 30 to 45-days after receiving their login, parents will be contacted via phone, email, and/or at follow-up clinics and will be provided a link to the REDCap site to complete the post-intervention questionnaires. Participants will also be given the option to meet with study staff via videocall if they would like to orient the participant to the REDCap site and provide technical support.

Follow-up 2 (6 months after baseline)

Approximately 6 months after receiving their login, parents will be contacted via phone, email, and/or at follow-up clinics and will be provided a link to the REDCap site to complete the long-term follow-up measures. Participants will also be given the option to meet with study staff via videocall if they would like to orient the participant to the REDCap site and provide technical support.

Brief interview

A subset of participants may be contacted via phone, email, and/or at follow-up clinics to complete a brief qualitative interview (10-15 minutes) about their experience with the intervention that may be audio recorded. This interview will be conducted anytime after follow-up 1 and may be done via email, phone, or in-person.

4.1.6 Participant Withdrawal or Termination

4.1.6.1 Reasons for Withdrawal or Termination

Participants are free to withdraw from the study at any time upon verbal or written request.

An investigator may terminate participation in the study if:

- Any adverse event, medical condition, or situation occurs such that continued participation in the study would not be in the best interest of the participant
- The participant meets an exclusion criterion (either newly developed or not previously recognized) that precludes further study participation

4.1.6.2 Handling of Participant Withdrawals or Termination

Participants are free to withdraw from the study at any time upon verbal or written request. If a family indicates they would like to withdraw, they will be given the option to discontinue intervention modules but remain in the study for follow-up or discontinue from the intervention modules and future follow-up. Existing data will remain in the study database. If a participant wishes to have all research being conducted on his/her data stopped, the data will not be included in the analysis.

5. Statistical and Analytical Approaches

5.1 Statistical and Analytical Plans

Caregiver functioning is examined as the primary and most proximal outcomes of the R2R-TBI intervention. Through targeting caregiver functioning, we expect the R2R-TBI intervention to have downstream effects (through reductions in caregiver depression and distress) on the secondary outcomes of child recovery and family functioning. We further anticipate that the same risk and protective factors that have been shown to moderate child recovery and the efficacy of other family-centered interventions for pediatric TBI, such as household income and baseline family functioning, will moderate the efficacy of the R2R-TBI intervention (e.g., Antonini et al., 2014; Raj et al., 2014b; Wade et al., 2012, 2015). Specifically, we anticipate that the R2R-TBI intervention will be most effective among low-income families and among caregivers with high levels of baseline distress. Our hypotheses are as follows:

Hypothesis 1: Caregivers receiving the R2R-TBI intervention will report lower levels of depression, anxiety, post-traumatic stress, and higher levels of caregiver self-efficacy and mindful self-care at follow-up, compared to caregivers in the IRC condition, after controlling for baseline levels.

The R2R-TBI intervention is designed to promote caregiver psychological well-being and positive parenting in the acute phase post-injury. This hypothesis represents an important test of whether the intervention is successful in improving these areas of functioning that are targets of the intervention. To evaluate this hypothesis, we will examine group difference in caregiver depression (CES-D-10, Radloff, 1977), anxiety (PROMIS Anxiety 4a), post traumatic stress (PC-PTSD-5, Prins et al., 2015), caregiver self-efficacy (CSES, Boothroyd & Evans, 1997), and mindful self-care (MSCS-25; Cook-Cottone, 2015) at one and six-months post-baseline, controlling for baseline scores. Given the challenges in the acute phase post-injury, we expect caregivers in the R2R intervention to report stable functioning while caregivers in the IRC group to report increasing levels of depression and distress at both one and six-month follow-ups.

Hypothesis 2: Caregivers receiving the R2R intervention will report better child and family functioning at follow-up, compared to caregivers in the IRC condition, after controlling for baseline functioning.

We anticipate that the R2R-TBI intervention will be effective in both ameliorating problems evident at baseline and in preventing emergence of additional problems in family and child functioning at one and six-months post-baseline. To test this hypothesis, we will examine group differences in family functioning (FAD-GF, Epstein, Baldwin, & Bishop, 1983), family burden of injury (FBI, Burgess et al., 1999) and child socioemotional functioning (PedSQL Psychosocial Summary Score, Varni et al., 1999) at one and six-months post-baseline.

Hypothesis 3: We hypothesize that treatment effects will be moderated by household income and level of caregiver distress at baseline.

We expect families with greater social disadvantage (lower income, more stress) will benefit most from the R2R-TBI intervention. This hypothesis is consistent with previous research findings (e.g., Antonini et al., 2014; Raj et al., 2014b; Wade et al., 2012, 2015).

Variable distributions will be examined before carrying out inferential statistical procedures, and transformations will be made in cases where distributions are skewed or fail to meet the assumptions of normality. Non-parametric procedures will be employed in cases where transformations would be inappropriate or where analysis of frequencies is justified. Preliminary work will also involve computation of reliabilities and creation of derived variables that summarize performance on measures that are highly inter-correlated. To evaluate potential attrition bias, caregivers who drop out (i.e., those who access < 3 modules and/or who do not complete baseline or follow-up measures) will be compared to those who remain in follow-up on background characteristics as well as on outcomes measured prior to dropout. Factors related to dropout will be included as covariates in the analysis.

Analytic plan for hypotheses 1 and 2. The primary analysis will consist of a linear mixed-effect models used to examine changes in caregiver, family, and child functioning among participants in the R2R-TBI intervention and IRC groups from baseline to 6-months post-baseline. In addition, the one-month data will be included in a mixed model repeated measures analysis. This model allows for flexible modeling of the pattern of change in outcomes over time and uses all the data for a given participant, even if that participant is not seen at all assessments, allowing us to retain participants with missing assessments.

Analytic plan for hypothesis 3. Existing literature and findings from our other studies suggest that demographic factors such as household income as well as baseline caregiver functioning impact adaptation to injury, and we hypothesize that these factors will moderate the efficacy of the intervention. Hierarchical multiple regression analyses which include the interaction of group, moderator (household income, baseline functioning), and time in the model will be used to test hypothesis 3. Variable selection using backward elimination will be used to remove non-significant higher- and then lower-order terms. In order to avoid selection bias, bootstrapping will be used on the backward elimination process (Austin, 2008). Post hoc analyses will be used to compare

treatment groups on each outcome at different levels of the moderators at 1 and 6-months post-baseline.

6. Data Management

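### The dropout rule counts module use, which control caregivers cannot have, and its covariate rule admits month-1 scores, which could bias a baseline-adjusted 6-month effect

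*Combined protocol and SAP*

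**What the plan says.** Section 5.1 sets out an attrition check in which "caregivers who drop out (i.e., those who access < 3 modules and/or who do not complete baseline or follow-up measures) will be compared" with those who remain in follow-up. The definition is not limited to one arm. The comparison covers background characteristics "as well as on outcomes measured prior to dropout. Factors related to dropout will be included as covariates in the analysis". Nothing restricts those covariates to variables measured before randomisation.

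Three other parts of the plan bear on this:

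- **Control arm content.** Section 4.1.3.2 states that "families in the IRC condition will have access to the same links to resources without the specific intervention content/modules".
- **Stopping modules versus leaving the study.** Section 4.1.6.2 keeps these apart: a family may "discontinue intervention modules but remain in the study for follow-up".
- **Form of the efficacy model.** For Hypothesis 1, section 5.1 compares the groups "at one and six-months post-baseline, controlling for baseline scores". The analytic plan for Hypotheses 1 and 2 then names "linear mixed-effect models used to examine changes in caregiver, family, and child functioning" from baseline to 6 months, and continues: "In addition, the one-month data will be included in a mixed model repeated measures analysis". It does not say whether baseline is a response or a covariate in the first of these models.

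**The concern.** There are two linked problems.

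**The definition of dropout.** Read as written, every control caregiver has accessed fewer than three modules and so is a dropout, even with every form returned. The attrition check then largely compares arms and cannot show who was lost to follow-up. If the module test was meant for R2R-TBI only, the rule still merges adherence with missing data. A low user who returns every form is then both a dropout and someone who remains in follow-up, and this can happen in one arm only.

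**The covariate rule.** For a caregiver who returns month 1 and misses month 6, the month-1 score is an outcome measured before dropout. If it is associated with dropout, the rule makes it a covariate. For someone flagged only by module count, the plan gives no dropout date, so whether month 1 counts is undefined. Month 1 comes after randomisation, and section 5.1 expects the arms to differ by then. Adjusting the 6-month comparison for it can remove part of the effect the trial is meant to estimate.

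**Working it through.** The plan gives no effect size, SD, correlation, dropout rate or power, so there is no stated figure to reproduce.

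**Inputs from the plan:** up to 200 participants (section 3.5), allocated with equal probability, so about 100 per arm; visits at baseline, 1 month and 6 months (section 3.1).

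**Assumptions:** effect at month 6, d6 = 0.40 SD; equal correlation rho between visits, 0.4 to 0.7; 20% missing at month 6; a share p = 20–40% of R2R-TBI caregivers below three modules; two-sided 0.05.

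**Step 1. Who is flagged when no forms are missing.**

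- Literal reading: (1 + p)/2 of the sample. For p = 0.2, 1.2/2 = 60%, or 120 of 200; for p = 0.4, 1.4/2 = 70%, or 140 of 200. Controls are 100/120 = 83% and 100/140 = 71% of those flagged, and none is in the retained group.
- R2R-only reading: p/2, which is 10–20%, or 20–40 of 200, all in one arm.

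**Step 2. Effect of adding month 1 to a baseline-adjusted (ANCOVA) model.** Under equal correlation, the slope of month 6 on month 1 given baseline is (rho − rho²)/(1 − rho²) = rho/(1 + rho). With d1 the month-1 effect, the adjusted group effect is d6 − d1 × rho/(1 + rho). With d6 = 0.40:

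| rho | slope | d1 = 0.40 | d1 = 0.20 | d1 = 0 | d1 = −0.20 |
|---|---|---|---|---|---|
| 0.4 | 0.286 | 0.29 | 0.34 | 0.40 | 0.46 |
| 0.6 | 0.375 | 0.25 | 0.33 | 0.40 | 0.48 |
| 0.7 | 0.412 | 0.24 | 0.32 | 0.40 | 0.48 |

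The bias is towards zero if the effect has the same sign at both visits, absent if there is no month-1 effect, and upwards if the month-1 effect is opposite. In simulation (2,000 runs per setting, 0.40 SD at both visits), power was 76–94% without month 1 and 49–60% with it.

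**Step 3. The other model form.** With baseline and month 6 both as responses, a month-1 main effect takes the same value on both of a caregiver's rows. It therefore cancels from the group-by-time contrast when data are complete. With 20% missing, a random-intercept model gave 0.365/0.364, 0.376/0.376 and 0.417/0.418 without/with month 1 at the three correlations. With only 120 runs each, the third decimal is noise (Monte Carlo error about 0.011–0.016); the point is that the paired values agree.

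**Step 4. How often month 1 would be selected.** Selection here means p < 0.05 in a t-test of dropouts against the rest, treating month 1 as observed before dropout for everyone, with 0.40 SD at both visits. The average estimate is from the ANCOVA form, over all trials whether or not month 1 was selected.

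| Definition of dropout | Month-6 missingness | Selected | Average estimate |
|---|---|---|---|
| Literal | unrelated to month 1 | 32–49% | 0.31–0.36 |
| R2R-only | unrelated to month 1 | 7–17% | 0.37–0.39 |
| Missing forms only | odds ratio 1.5 per SD of month 1, either direction | 61–65% | 0.29–0.33 |

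The last row shows that correcting the dropout definition alone does not cure the covariate rule.

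**The case against.** The strongest reply is that the bias needs a model the analytic plan does not clearly describe. A mixed model from baseline to 6 months with baseline as a covariate leaves one response per caregiver and no caregiver-level random effect to estimate. The natural reading has baseline as a response, and then there is essentially no shrinkage. In the additional repeated-measures model, month 1 is already a response and would not sensibly also be a covariate. This stands as far as it goes. However, section 5.1 says three times, across Hypotheses 1 and 2, that the comparison controls for baseline, so the baseline-adjusted form remains open.

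Second, no analyst would label all 100 controls as dropouts, so the literal-reading figures deserve little weight. That is fair. On the R2R-only reading, with missingness unrelated to month 1, the average loss is small (0.37–0.39 against 0.40). That reading still mixes adherence with attrition in one arm.

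Third, the dropout label removes nobody from the analysis, and month 1 is admitted only by silence. A month-1 covariate would also be missing for anyone without that visit, against the plan's aim of retaining such participants. All true, but these are reasons to write the restriction down. The 61–65% selection figure comes from the covariate rule and an assumed missingness pattern, and should not be charged to the module criterion.

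**Conclusion.** Both parts hold. The dropout definition is defective on either reading: it makes every control a dropout, or it counts non-use as attrition in one arm. The covariate rule permits, but does not require, adjustment for a post-randomisation outcome. If month 1 is selected, the 6-month comparison is baseline-adjusted, and the effect is 0.40 SD at both visits, the estimate falls by rho/(1 + rho), or 29–41% for rho 0.4 to 0.7. With baseline as a response and a group-by-time contrast it is essentially unchanged.

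The likely average loss ranges from slight to about a quarter (0.29 against 0.40), depending on the dropout definition and on whether missingness tracks month-1 scores. Every figure except the 200 total is assumed. This should be corrected, but it is not fatal to the trial. One further clause is redundant but harmless: missing baseline measures cannot define dropout after randomisation, because section 4.1.2 says "Once study staff receive complete baseline forms, participants will be randomly assigned".

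**What to change.** In section 5.1:

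1. Define attrition identically in both arms as a missing month-1 or month-6 outcome form, and drop the baseline clause.
2. Report module use separately, as adherence within R2R-TBI.
3. Limit added covariates to pre-specified variables measured before randomisation, for example baseline score, age stratum, severity stratum and income.
4. Use month-1 scores only as responses in the repeated-measures model, never as covariates.
5. State whether the 6-month effect is a baseline-adjusted difference or a group-by-time contrast.

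The cost is SAP wording only: no new data and no additional participants.

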3.5 Recruitment Procedures

Up to 200 participants will be enrolled in this RCT. Potential participants will be identified and recruited from the CCHMC and NCH Trauma Registry, inpatient units, and outpatient clinics such as rehabilitation clinics. Potential participants will also be recruited through sharing of study information and study flyer at other hospitals and through organizations and associations serving children/families impacted by pediatric TBI.

Recruitment at CCHMC and NCH

Parents/caregivers who are eligible to participate will receive the study brochure or flyer while they are at the hospital, when their child is discharged from the hospital and/or at follow-up visits or clinics. Eligible parents/caregivers may also receive the study brochure or flyer via mail and or email (see recruitment email). The study brochure and flyer includes a QR code to a website that has the information sheet for the study. Research personnel will connect with families at the hospital (e.g., at follow-up clinics or discharge) or via phone (see phone /in-person recruitment script). Parents will be provided information about the study during this contact and will have the opportunity to review the information sheet/consent form and ask questions. Study staff will document this consent process on a form that will be included in the study binder.

Recruitment through sharing of study information and flyer

Potential participants may also reach out to the study staff and request to be screened for the study. Study staff at CCHMC will screen potential participants for eligibility and families who meet criteria will be provided information about the study during this contact and will have the opportunity to review the information sheet/consent form and ask questions (see Road-to-recovery telephone script for potential participants who self refer). Study staff will document this consent process on a form that will be included in the study binder

For all

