If the parent or individual is not interested, they will be thanked for their time and no further contact about the study will be made. If interest in the study is expressed, the parent will be sent a link to the study REDCap site. Parents will also be given the option to meet with study staff via videocall to orient the parent to the REDCap and/or study site and provide technical support. The study REDCap site opens with the study information sheet that provides contact details for study personnel. Participants who choose to participate will indicate consent by clicking a button at the bottom of the REDCap information sheet that reads, “YES, I acknowledge that I have viewed the information sheet and am voluntarily choosing to participate in this study.” Participants who click “YES” will then begin the baseline questionnaires. Participants who choose not to participate will click the “NO, I acknowledge that I have viewed the information sheet and I do not wish to participate in this study,” and they will receive a notification thanking them for their time and they will not be able to access the questionnaires.

After baseline measures have been completed, the predetermined randomization sequence will be used to randomize caregivers into one of the two conditions (R2R-TBI vs. IRC). Stratified randomization will be used to achieve balance in child’s age (< 5 years; ≥ 5 years) and injury severity. The randomization sequence will be based on a design with blocks of four or six chosen randomly within the sequence with equal probability. A pseudorandom number generator in R will be used, and the randomization sequence will be maintained by the statistician. Randomly varying block size reduces the chance that research staff will guess the next group assignment, minimizing unconscious bias. Block randomization with randomly mixed block sizes will then be performed with equal probabilities of assigning a participant to one of the two intervention groups.

4. Study Procedures

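### The dropout comparison that selects covariates for the hypothesis 1 and 2 models has no by-arm element; prespecifying household income is a free improvement

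*Combined protocol and SAP*

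**What the plan says.** Section 5.1 (Statistical and Analytical Plans) holds the whole attrition plan. It defines dropout as "caregivers who drop out (i.e., those who access < 3 modules and/or who do not complete baseline or follow-up measures". Those caregivers "will be compared to those who remain in follow-up on background characteristics as well as on outcomes measured prior to dropout". The result then feeds the model: "Factors related to dropout will be included as covariates in the analysis". The text does not mention arm, gives no criterion for what counts as related, and names no sensitivity analysis for missing data.

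The hypothesis 1 and 2 analyses are mixed models that control for the baseline score of the outcome and use all available visits. Household income is not a named covariate in them. It is collected in the baseline demographic survey (section 3.3), but the stratification factors are child's age and injury severity (section 3.5). It appears by name only as a moderator for hypothesis 3, where the plan states that "demographic factors such as household income as well as baseline caregiver functioning impact adaptation to injury".

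On size and timing, section 3.5 says "Up to 200 participants will be enrolled in this RCT", with "equal probabilities of assigning a participant to one of the two intervention groups". It also says "After baseline measures have been completed, the predetermined randomization sequence will be used to randomize caregivers". On the comparator, section 4.1.3.2 says that "families in the IRC condition will have access to the same links to resources without the specific intervention content/modules".

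**The concern.** In a two-arm trial, attrition threatens the result when the caregivers who remain in one arm differ prognostically from those who remain in the other. Comparing dropouts with stayers without regard to arm answers a different question: who drops out overall. A factor that raises dropout equally in both arms will be flagged although it does not disturb the contrast. A factor that raises dropout in one arm and lowers it in the other can average out, go unflagged and so be left out of the model.

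At stake is a modest bias in the arm contrast, together with a primary model whose covariates are chosen from the data. The plan itself regards income as prognostic, yet for hypotheses 1 and 2 income enters only if this screen picks it up.

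**Working it through.** **Inputs.** From the documents: at most 200 caregivers, allocated 1:1, so 100 per arm. The documents state no dropout rate, alpha, SD or effect size, so there is no planned figure to reproduce. Assumed: 25% dropout in each arm; a standardised baseline factor acting on dropout with a log-odds slope of 0.8 where it acts, which puts dropouts about 0.53 SD from the mean; a two-sided 5% test; and a prognostic effect of 0.2 to 0.3 SD of outcome per SD of factor.

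**Step 1. What dropout does within an arm.** Stayers' mean = −(0.25 × 0.53)/0.75 = −0.177 SD. Dropouts minus stayers = 0.53 + 0.177 = 0.707 SD.

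**Step 2. How often the comparison flags the factor.** Ignoring arm, there are 50 dropouts and 150 stayers, so SE = √(1/50 + 1/150) = 0.163, taking the SD as 1. With equal dropout rates, the overall difference is the average of the two arms' differences.

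| Dropout slopes (R2R-TBI / IRC) | Overall difference | z | Flagged, approximate | Flagged, simulated |
|---|---|---|---|---|
| 0.8 / 0.8 | 0.707 | 4.33 | 99% | over 99% |
| 0.8 / −0.8 | 0 | 0 | 5% | 5.0% |
| 0.8 / −0.4 | – | – | – | 17% |
| 0.8 / 0 | 0.707/2 = 0.353 | 2.16 | 58% | 58% |

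For one-arm selection, separate simulations under somewhat different assumptions ranged from 55% to 79%.

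**Step 3. The by-arm alternative.** The arm-by-dropout contrast has SE = √[2 × (1/25 + 1/75)] = 0.327. Opposite slopes give 1.414/0.327 = 4.33, so about 99% flagged (simulated 99.4%). One-arm selection gives 0.707/0.327 = 2.16, so about 58%, no better than the comparison that ignores arm.

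**Step 4. Bias in the extreme cancelling case.** Stayers differ between arms by 2 × 0.177 = 0.353 SD on the factor. Multiplying by 0.2 to 0.3 gives 0.071 to 0.106 SD. Simulations that follow the plan, with the baseline score in the model and the factor added only when flagged, gave 0.065 to 0.097 SD. With an effect of 0.3, one run gave a bias of −0.094 and a type I error of 0.105; always adjusting for the factor gave about 0 and 0.045. With slopes of ±0.5 the bias was 0.04 to 0.06 SD. With the same slope in both arms it was about 0 with or without adjustment.

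**Step 5. When there is no bias.** In simulations with about 22% dropout overall and a prognostic effect of 0.4, dropout of 35% versus 10% unrelated to the factor gave a bias of +0.002. Opposite-direction dropout on the baseline outcome, already in the model, gave 0.

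**Step 6. Gain from always adjusting.** Even where there was no bias, the standard error of the treatment effect fell from 0.131 to 0.124: (0.131 − 0.124)/0.131 = 5%.

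**Step 7. The dropout definition.** IRC has no modules, so the module criterion separates caregivers only in R2R-TBI. Taken literally, it makes every IRC caregiver a dropout. Applied to R2R-TBI alone, it weights the dropout group to that arm and can include caregivers with complete outcomes. At 35% versus 15% dropout with slopes of ±0.8, the comparison flags 19% rather than 5%. Caregivers who do not complete baseline have no arm, because randomization comes later.

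**The case against.** Four objections have force.

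- **Silence is not pooling.** A reader might infer that the plan mandates a comparison pooled over arms and is wrong as written. It says neither that nor the opposite. What the text supports is that no by-arm comparison is specified.
- **The screen is not blind to arm-specific dropout.** One-arm selection is arm-specific, and the screen finds it about as often as an interaction test does. Near-total failure needs roughly equal and opposite patterns at similar rates. Nothing in the documents says that any factor will behave so. R2R-TBI's interactive modules and weekly reminders, against links alone in IRC, make differing patterns possible but not predicted.
- **Arm-specific dropout does not by itself bias the contrast.** It must also be tied to an omitted prognostic factor or to unseen outcomes (step 5), and the mixed model already covers the baseline outcome.
- **The cancellation argument depends on how dropout is defined.** It cannot be said to hold under any definition; step 7 shows how the module criterion alters it.

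It is also fair that an interaction test is no safeguard: at about 58% for one-arm selection, a non-significant result proves little. And fixing income in advance protects against one factor only. What stands is that a screen without an arm dimension is a poor rule for choosing covariates when a baseline variable the plan considers prognostic is already to hand.

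**Conclusion.** A free improvement, not an error that invalidates the plan. The documents do not support a claim that the primary result will be biased. They support a narrower one: the covariate rule responds to a harmless pattern and responds weakly, at 5% to 58% under the assumptions above, to patterns that can do harm. The resulting bias is at most about 0.07 to 0.10 SD, in the extreme cancelling case with a prognostic effect of 0.2 to 0.3.

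The dropout rate, slopes and prognostic effect are all assumptions, and 200 is a ceiling on enrolment, so the sizes are illustrative and the direction is the finding. The case for prespecifying income does not depend on the extreme case, because a prognostic covariate also bought about 5% in standard error where there was no bias to remove.

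**What to change.** 1. **Prespecify household income** as a baseline covariate in the hypothesis 1 and 2 models, with its coding stated, instead of leaving it to the dropout comparison. It is already collected, so the cost is one sentence in section 5.1.
2. **Redefine dropout for the attrition check** as missing follow-up outcomes only. Report it by arm and visit, and examine its predictors with an arm interaction. Present this as description, not as a test whose non-significance gives an all-clear. The cost is revised text and a few extra models, with no new data.
3. **Optionally, add one sensitivity analysis** that shifts the imputed six-month scores of non-returners by an arm-specific amount until the conclusion changes. Neither step above deals with dropout driven by unseen outcomes: in a simulation of that pattern in R2R-TBI only, the bias was −0.097 under the plan and still −0.079 after adjusting for the factor, and the arm interaction flagged 20.2% of trials. This is the costlier item, because the plan has no imputation step and hypotheses 1 and 2 name eight outcomes.
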